A9. ClinicalTrials.gov Registration

Does this protocol/trial require registration on ClinicalTrials.gov due to it: meeting the definition of an Applicable Clinical Trial, being required under the terms and conditions of an award, or being proposed to be published in ICMJE journals? Yes

Who will be responsible for registering and maintaining the registration of this Applicable Clinical Trial? The BCM PI will register the trial because either:

- the trial is BCM PI-initiated,
- BCM is the lead site of this multicenter trial, or,
- the industry sponsor has instructed the BCM PI to register the trial, or,
- registration of this trail is required as a term and condition of the reward by the funding agency.

ClinicalTrials.gov Identifier: NCT04307355

Section B: Exempt Request

B. Exempt From IRB Review

Not Applicable

Section C: Background Information

Reduction mammoplasty is a procedure in which a volumetric reduction of the breast is done for cosmetic purposes. This technique includes an infra-mammary perpendicular incision joined by a T-inframammary fold in it; central area, that further continue vertically until surrounding the nipple perimeter.

The likelihood of poor healing outcomes and adverse events (e.g., wound dehiscence, thick scar, itchy or unsortable scars) at the T-inframammary fold (anchor incision) of the breast wound incision is relatively high (estimated to be 10%-15%). This pure outcome is attributed to the corner (as a result of the T-inframammary fold) low blood supply. Given the fact that there are two corners in this particular procedure, the chances of adverse events are higher due to the point of most tension for the entire breast. Continuous oxygen therapy may reduce the likelihood of poor outcomes and adverse events.

In our institution, the Plastic Surgery Department utilizes Dermabond glue (sano acrylic) and Prineotape (air and water sealed) to close the wound around the areola and over the T-inframammary fold. Depending on the incision size, a JP drain could be placed (10% of the cases). Furthermore, the Prineo tape is kept on for a period of 3 weeks. Once it is removed, the incisions are normally healed. However, if wound dehiscence presents, it normally happens between the second and third post-operative week. Then, the Prineo tape has to be removed before the expected time period. Therefore, an external dressing might be able to avoid wound dehiscence during this period.

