1) Baseline (Surgery Day, Week 0) 2) Visit 1 (Week 1 Post-Op) 3) Visit 2 (Week 2 Post-Op) 4) Visit 3 (Week 3 Post-Op) 5) Visit 4 (Week 4 Post-Op) 6) Visit 5 (minimum of 6 months Post-Op) *optional

Baseline: Subjects will be randomized to internal control. Since all procedures are bilateral, an internal randomization will be performed based on breast side (left or right). The patients will be given CDO in one breast defined as intervention breast. A 5x5 cm CDO dressing will be placed by the plastic surgeon over the T-inframammary fold after the Dermabond glue and Prineo tape are placed. Then, Silagen (a silicon sheet) will be placed on top of the CDO dressing to secure it in place. The remaining parts of the incision will be covered with Dermabond Glue and Prineo tape. On the contrary, the control breast will be given the standard dressing (Dermabond + Prineo tape).

Visits 1-4: All patients will have baseline assessment including visual, dermal, and tissue oxygen saturation level. The status of wound closure and presence of wound complication will be monitored every week. Each subjects will need up to 5 visits including baseline assessment, and weekly assessment up to 4 weeks or full wound healing or surgical revision, whichever comes first. At each visit, patients will be provided standard of care treatment including regular wound dressing change. Table 1 in attachments' section summarizes the key measurement at each study visit. At Visit 4, the CDO therapy will be removed. Subjects will then have the option to return at minimum 6 months later for a final follow-up visit listed below.

Visits 5: Optional follow-up visits. This visit can also be done remotely should the person not be available to attend the clinic.

Inclusion Criteria:

18-85 years of age. Ability to provide informed consent. Presence of a wound due to surgical intervention and closure. Subject or responsible caregiver is willing and able to maintain the required Continuous Diffusion of Oxygen (CDO) system (if assigned to the intervention group) and applicable dressing changes

Exclusion Criteria:

Active Drug/alcohol abuse (or history of drug/alcohol abuse in last 1 month); excessive lymphedema; presence of active infection; subject has a history of or any intercurrent illnesses or conditions that would compromise the safety of the subject according to judgement of a qualified wound specialist.

F2. Procedure

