Please note that subjects will be consented before performing any study related measurements. This study will not bring any direct costs to the subject. The subject's medical insurance will be billed for all standard of care procedures.

Eligible subjects will be internally randomized and will receive the intervention for 4 weeks. Each subjects will receive standard of care for wound treatment. Intervention side will receive adjunct Continuous Diffusion of Oxygen (CDO) therapy using a novel dressing, which facilitates continuous supply of oxygen to the wound inside the wound dressing using a portable device named OxyGeni . We will collect patient demographics (e.g., age, sex, height, weight, race, ethnicity, marital status, level of education, etc), relevant medical history (e.g., comorbidity, type of surgery, number of prescription and over counter medication, etc), and relevant social factors (e.g., marital status, years of education, type of work, tobacco history, etc) at baseline. Primary outcomes include tissue oxygenation (assessed using Kent Imaging system) and incidence of wound complications (e.g. dehiscence, infection, and surgical revision). Primary outcomes will be assessed at baseline and on a weekly basis for up to 4 weeks. Secondary and exploratory outcomes include inflammation (assessed using a KENT camera), pain (assessed visual analog scale). The secondary and exploratory outcomes will be assessed at baseline and week-4. Other optional assessments include quality of life (NIH Global Health PROMIS), depression (Center for Epidemiologic Studies Depression Scale, CES-D), cognitive function MoCA), and psychosocial metrics (e.g. fatigue, anxiety, frailty, sleep, etc). These assessments are optional and will be done upon time availability and patient acceptance. We anticipate that duration of all assessments will not exceed 60 minutes. We will be reviewing the billing records for our

patients to explore costs of both groups. We may visit the patient's home for an appointment that doesn't require the physician present or to fix any issues with the device.

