There will be an optional follow up visit up to three and six months after the last visit to determine any potential wound complications (e.g., patient unhappiness with the appearance of scar, infection and quality of life etc). During this visit, study coordinator will photograph both incision sites using near-infrared spectroscopy (NIRS, KENT camera) and a digital photo. Practitioner will assess scarring using the SCAR and/or POSAS scale.

Dressing Change: All patients will have their dressing changed weekly (screening/initial visit and visits 1-4), the intervention site will be treated continuously with oxygen from the OxyGeni device. Prior to application of the OxyGeni, research staff will: Select a 5x5cm OxySpur O2 dressing that will cover the wound; Wrap dressing as directed by physician. This may facilitate delivery of oxygen to the incision site or wound bed.

Data collection: - Medical History: Relevant patient medical history (e.g. type of cancer, type of therapy, other comorbidity such as diabetes and stroke, history of surgery, number of prescription and over counter medication, etc) will be collected at baseline via questionnaire or patient electronic health record.

- Social Factors: marital status, years of education, type of work, tobacco history (pack years, current smoker, current use of chewing tobacco, previous smoker, no tobacco history), drug history (current, previous history, no drug history), and alcohol history. These factors will be collected at screening/baseline visit.

Tissue Oxygen Saturation (primary outcome): Tissue oxygenation level will be assessed using Kent Imaging system at baseline and every study visit. The device uses light in the near-infrared spectrum that harmlessly passes through the skin and reflects off the blood supplying the tissue to determine tissue oxygen saturation, a key indicator of tissue health. The NIRS light has two key features that make it useful for measuring the viability of living tissue. Firstly, NIRS light is not absorbed by tissue as much as visible or ultraviolet light. Secondly, NIRS light is mainly absorbed by hemoglobin and water. Most importantly, the wavelength dependent light absorption of hemoglobin differs if it is carrying oxygen from when it is not. This makes NIRS light very useful in detecting oxygenated and deoxygenated blood, which conveys a comprehensive picture of tissue health and the healing capacity of wounds or tissue transplants.

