Wound Assessment (primary outcome): A digital photo/video of wound will be taken for wound size verification, estimation of wound size, success of wound healing, and determination of wound dehiscence. Measurement will be performed at every visit.

Pain Intensity Assessment (VAS) (secondary outcome): The subject will be provided with a numeric pain scale where he/she will report pain intensity. Research staff will document subject's pain level. (Collected at every visit)

Adverse Event Reporting: Research Staff will document and report any study/non study related incident as per institution regulations. (Collected at baseline and visits 1-4)

Device Acceptability Questionnaire: To determine patient perception of benefit, perceived ease of use, and attitude toward the use of device, we will use a technology acceptance model (TAM) questionnaire tailored for the purpose of this study. This assessment will be done at the conclusion of the study (week-4)

Questionnaires (optional): Quality of Life (PROMIS), functional status, Frailty Status (TSFI), Cognitive Assessment, and Sleep Quality (PSQI). To evaluate functional status, we will use well accepted and validated general functional assessment instruments. PFIBS for Pain Frequency, Intensity and Burden Scale, MOCA for Mental Exam, and Visual analog scale for pain. (All questionnaires are optional and may be done at any study visit upon time availability and patient acceptability). We will add the already approved questionnaires for the parent study, which include pain. Additionally, we will include Likert Scales (Moon SH et al, 2011; Singer AJ et al 1997; Hollander JE et al 1995; and Ridway DM et al 2007) and Patient Attitude to Scarring Scale (PASS, Kantor J et al 2016) and Patient and Observer Scar Assessment Scale (POSAS) to assess the following patient-reported outcomes: patient satisfaction and cosmetic appearance to evaluate scar itchy, perception of scar thickness, scar discomfort, and pain for each wound side (i.e., left and right breast). SCAR may be used to assess plastic surgeon satisfaction with the scarring. These questionnaires will be answered to the best of the participant's abilities. Should the participant lack certain capacities that make it difficult for them to respond to these questionnaires, they will not be conducted with that participant.

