The plastic surgeon ([name]) will perform the initial consultation with the patient in the clinical setting (initial and pre-operative consult). Once the patient is aware of the study protocol, the study coordinator will obtain consent on the day of surgery. Research coordinators are responsible to revise the medical records (e.g., Epic) on a weekly basis in order to screen possible candidates undergoing reduction mammoplasty that could fit for the study. If the patient fits the criteria, the research coordinator will communicate the candidate's information (e.g., name, date of surgery) to [name]. Candidates will be consented on the day of surgery upon plastic surgeon approval.

Baseline visit: After consenting the patient, the research coordinator will attend to the surgery. When the plastic surgeon closes the incision, the research coordinator will obtain the tissue oxygenation image using (non-invasive) NIRS, and then the surgeon will place the dressing immediately (The CDO dressing will be applied on the T-inframammary fold of the breast incision), followed by Silagen directly on top. After surgery, the research coordinator will wait until the patient is coherent in the post-operative recovery area. Then, they will educate the patient on proper device use.

After the surgery, the study will include 4 weekly follow-up visits, with visits in between for additional dressing changes asneeded. The 4 weekly follow-up visits are described below.

Visit 1, 1 Week Post-Op *duration: 50 minutes. Research staff will perform tasks as described above: Pain Questionnaire, NIRS Imaging, Digital Photograph, Adverse Event Reporting, Wound Assessment, Dressing Change and Device Education. Plastic surgeon will remove the CDO dressing in his normal post-operative clinic appointment, and the female research coordinator will obtain the near-infrared spectroscopy image, digital image, and wound assessment. After that, the research coordinator will cover the incision with a new CDO dressing. All measurements and procedures will be performed by a female research coordinator under ethics protocols.

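### Inflammation is scheduled for reading only at closure and at week 4, although Kent images are already planned at weeks 1, 2 and 3; the timing of pain needs reconciling within F2

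*Combined protocol and SAP*

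**What the plan says.** F2 (Procedure) lists the outcomes in question: "Secondary and exploratory outcomes include inflammation (assessed using a KENT camera), pain (assessed visual analog scale"). It then gives their timing: "The secondary and exploratory outcomes will be assessed at baseline and week-4". The sentence on the primary outcomes, just before, puts those on a weekly schedule.

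The other relevant statements are:

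- **Baseline.** F1 (Design) defines it as "Baseline (Surgery Day, Week 0"). F2, under the baseline visit, says: "When the plastic surgeon closes the incision, the research coordinator will obtain the tissue oxygenation image using (non-invasive) NIRS". The dressing goes on after that.
- **Healing.** Section C (Background Information) says: "Furthermore, the Prineo tape is kept on for a period of 3 weeks. Once it is removed, the incisions are normally healed". It adds that "if wound dehiscence presents, it normally happens between the second and third post-operative week".
- **Imaging.** F2, under tissue oxygen saturation, says: "Tissue oxygenation level will be assessed using Kent Imaging system at baseline and every study visit". The descriptions of visits 1 to 4 each list near-infrared imaging and a pain questionnaire.
- **Pain.** F2, under pain intensity assessment, says: "Research staff will document subject's pain level. (Collected at every visit").
- **Analysis.** G2 (Data Analysis) lists area of inflammation as secondary without time points, and gives a generic choice of tests for secondary and exploratory outcomes. It reserves a mixed model with time, group and their interaction for skin perfusion.
- **Early end.** F1 lets the weekly assessments stop before week 4 once the wound has healed fully or been surgically revised.

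**The concern.** An outcome meant to show what oxygen does to a healing incision is read once before treatment starts and once at its end. The end reading comes about a week after the point at which Section C expects incisions to be healed. Nothing is read in between, although the same camera is used on the same patients at each intervening visit.

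Two things are at stake. A difference in inflammation that exists during weeks 1–3 but has faded by week 4 could be missed. And repeated readings that would make the comparison more precise, in a study of 30 patients, go unused. A patient whose assessments stop early contributes no post-operative inflammation value at all under the stated rule.

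For pain the issue is different. F2 gives two schedules for the same measure, so it is unclear which scores enter the analysis.

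**Working it through.** The documents give no standard deviation, effect size or power for inflammation, and G1 sets n = 30 by resources. There is therefore no plan figure to reproduce. The check is a comparison of schedules followed by two short calculations.

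**Schedules side by side**

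| Time | Inflammation (F2 rule) | Kent/NIRS image (F2) | Pain (F2 rule) | Pain (F2 pain item and visit list) |
|---|---|---|---|---|
| Week 0 | yes, at closure | yes | yes | yes (pain item) |
| Week 1 | no | yes | no | yes |
| Week 2 | no | yes | no | yes |
| Week 3 | no | yes | no | yes |
| Week 4 | yes | yes | yes | yes |

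The stated rule uses 2 of 5 scheduled image times and 1 of 4 post-operative ones. Section C puts normal healing at about week 3, so the single post-operative reading falls 4 − 3 = 1 week later.

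**Images not used**

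With 30 patients, two breasts and four post-operative visits, 30 × 2 × 4 = 240 images. Weeks 1–3 account for 30 × 2 × 3 = 180, or 180/240 = 75%. This is a maximum. It assumes that every visit takes place and that both breasts are imaged each time; F2 says explicitly that both sites are imaged only for the optional late follow-up.

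**Precision**

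The comparison is within patient, so the unit is the CDO-minus-control difference at each visit. Let r be the correlation of that difference between visits, with equal variance at each visit. The ratio of the standard error of the mean of k readings to that of one reading is √[(1 + (k − 1)r)/k]. The documents give no value of r; 0.3 to 0.7 is an assumption.

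| r | k = 4 (weeks 1–4): √[(1 + 3r)/4] | Reduction | k = 2 (weeks 3 and 4): √[(1 + r)/2] | Reduction |
|---|---|---|---|---|
| 0.3 | √0.475 = 0.689 | 31% | √0.65 = 0.806 | 19% |
| 0.5 | √0.625 = 0.791 | 21% | √0.75 = 0.866 | 13% |
| 0.7 | √0.775 = 0.880 | 12% | √0.85 = 0.922 | 8% |

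The k = 2 columns show what remains if tape makes the week 1 and week 2 images unreadable for this purpose. Both sets of figures treat the effect as the same at every visit. If it is not, the gain cannot be summarised by a standard error alone: averaging helps detect an early effect that has gone by week 4, and dilutes one that appears only at week 4.

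**The case against.** Several points on the other side have force.

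- **Week 4 is a defensible choice.** F1 has the CDO therapy removed at visit 4, so this is the end-of-treatment reading. Baseline is a pre-treatment reference, and the absence of post-operative inflammation at closure is no fault in it. Both points stand, and both readings should be kept.
- **The time course of inflammation is not documented.** A reader might infer that both times necessarily miss inflammation, so that a real effect will come out as no difference. The documents do not support that. They never say when inflammation begins, peaks or resolves; the second-to-third-week window concerns dehiscence, and normal healing of an incision does not prove that inflammation has gone. What stands is that a difference confined to weeks 1–3 could be missed.
- **The images may not be readable.** Section C keeps the Prineo tape on for 3 weeks, and the visit 1 description mentions removal of the CDO dressing only. Whether an area of inflammation can be read with tape in place is not stated. The protocol relies on these images for a primary outcome, but that does not settle it. This needs confirming.
- **Another schedule may exist.** F1 refers to a Table 1 in the attachments, which is not in the text available here. If it schedules inflammation weekly, the F2 sentence conflicts with it and still needs correcting.
- **Pain is collected weekly.** A reader might infer a gap in pain data. There is none: the pain item and all four visit descriptions provide for it.
- **The stakes are limited.** This is a pilot, none of H1 to H5 names inflammation, and both primary outcomes are assessed weekly.

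**Conclusion.** The point holds as a cheap improvement to a secondary outcome. On the text available, F2 gives inflammation one post-operative reading, about a week after incisions are normally healed and possibly missing where assessment ends early. Images are already scheduled at the three visits left out. A difference during weeks 1–3 could go unseen, and repeated readings are wasted.

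The size is conditional. The 12% to 31% reduction in standard error assumes a constant effect, equal variances, four usable readings per breast, and a visit-to-visit correlation of the between-breast difference of 0.7 to 0.3. The count of 180 out of 240 is an upper limit. The conclusion that a difference in weeks 1–3 could be missed needs none of these figures. The usefulness of the remedy depends on whether the week 1–3 images can be read for inflammation.

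For pain the finding is an inconsistency within F2, with no loss of data collection.

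**What to change.** 1. In F2, replace the timing rule for inflammation with wording such as: *Area of inflammation will be read from the Kent images of both breasts at baseline and at weeks 1, 2, 3 and 4.* Baseline stays as the reference.
2. In G2, name the contrast: the within-patient CDO-minus-control difference over weeks 1–4. The repeated-measures mixed model already planned for skin perfusion could be used, provided that it keeps the pairing of breasts within patient and uses baseline as reference. Report week 4 separately as the end-of-treatment reading.
3. Before fixing this, confirm whether inflammation can be read with the tape in place. State in advance what makes an image unreadable, treat such images as missing, and report their number by visit and breast.
4. For pain, reconcile the two statements in F2 so that the weekly scores already collected are analysed, and carry the same time points into G2.
5. Check Table 1 in the attachments against the amended text.

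The cost is a few sentences in F2 and G2 and the time to read images that are already scheduled. No visit or imaging session is added. The downside is that some week 1–3 images may prove unusable, which would shrink the precision gain.

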Section D: Purpose and Objectives

This is an exploratory randomized controlled trial study to test feasibility, acceptability, and proof of concept efficacy of Continuous Diffusion of Oxygen (CDO) adjunct therapy for decreasing healing time and reducing tissue dehiscence post breast reconstruction. We will assess the benefit of this novel adjunct therapy on successful closure, tissue oxygenation, scar appearance, and patients centered outcomes including perception of benefit, pain, sleep quality, and quality of life. Since all procedures are bilateral, an internal randomization will be performed based on breast side (left or right). The patients will be given CDO in one breast defined as intervention breast. A 5x5 cm CDO dressing will be placed by the plastic surgeon over the T-inframammary fold after the Dermabond glue and Prineo tape are placed. Then, Silagen (a silicon sheet) will be placed on top of the CDO dressing to secure it in place. The remaining parts of the incision will be covered with Dermabond Glue and Prineo tape. On the contrary, the control breast will be given the standard dressing (Dermabond + Prineo tape). The study device OxyGeni is a Class II medical device which has US Food and Drug Administration (FDA) 510(k) clearance, CE-Mark approval and a Health Canada license for the treatment of wounds.

Outcomes will be assessed on weekly-basis up to 4 weeks. Here are the aims and hypotheses for this study:

Aim1: To assess effectiveness of CDO adjunct therapy in reducing the likelihood of wound complication post-surgical

closure.

H1: CDO adjunct therapy will reduce the likelihood of surgical wound complication including dehiscence and its volume, infection or surgical revision, compare to standard of care dressing.

Aim2: To assess changes in skin perfusion in patients treated with CDO adjunct therapy.

H2: CDO adjunct therapy will improve tissue oxygen saturation in >50% of the patients as compared to baseline (measurements at baseline, 2 weeks, and 4 weeks).

Aim3: To evaluate changes in quality of life, anxiety during dressing change, and psychosocial parameters in patients with a surgical wound treated by CDO adjunct therapy

H3: CDO adjunct therapy will improve subject quality of life, reduce anxiety, and reduce perceived pain and physiological stress response during dressing change compared to the control group.

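### The secondary pain rating names no breast, so read as written it cannot compare CDO with control; its schedule, scale and status also need reconciling

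*Combined protocol and SAP*

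**What the plan says.** **Design.** F1: "Since all procedures are bilateral, an internal randomization will be performed based on breast side (left or right"). Every patient has one CDO breast and one control breast.

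**Hypothesis.** H3 in Section D states that CDO will "reduce perceived pain and physiological stress response during dressing change compared to the control group".

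**Pain measure.** The pain intensity entry in F2, marked as a secondary outcome, reads "The subject will be provided with a numeric pain scale where he/she will report pain intensity" and continues "Research staff will document subject's pain level. (Collected at every visit"). No breast is named.

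**Pain by side.** The optional questionnaires paragraph of F2 adds scar scales (Likert, PASS, POSAS) covering, among other items, "scar discomfort, and pain for each wound side (i.e., left and right breast"). That paragraph makes all its questionnaires optional at any visit. The visit list makes PASS and POSAS optional at Visit 4 and includes them at Visit 5, which is itself optional.

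**Schedule.** The overview in F2 lists pain with the secondary and exploratory outcomes and then says: "The secondary and exploratory outcomes will be assessed at baseline and week-4". The Visit 1 description says: "Research staff will perform tasks as described above: Pain Questionnaire, NIRS Imaging, Digital Photograph, Adverse Event Reporting, Wound Assessment, Dressing Change and Device Education". The descriptions of Visits 2, 3 and 4 also list a pain questionnaire and a dressing change.

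**Analysis.** G2 lists pain twice among the secondary outcomes. It offers chi-square, repeated ANOVA or a Mann-Whitney-type test according to the variable's distribution. It states no side-to-side pain comparison.

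**The concern.** In a split-body design the outcome has to be recorded at the level that was randomized. Here that level is the breast. A single rating of how much pain the patient has mixes the treated and untreated sides, and no later analysis can separate them.

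The pain part of H3 would then rest on change over time alone. Every patient receives CDO on one side and every patient is recovering from surgery on both, so such a change cannot be attributed to CDO.

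Pain is the only clearly patient-reported item in G2's secondary list, and unlike quality of life it can be attributed to a side. This part of H3 can therefore be made testable, but only if the side is recorded when the rating is taken.

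**Working it through.** The plan states no figure for pain (no effect size, SD, alpha or power), so there is nothing to reproduce. The check sets the passages side by side and counts ratings.

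**Step 1. What an unsided score can show.** Let C be pain in the CDO breast, K pain in the control breast, and S = g(C, K) the single score reported.

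- Within a patient there is one S per visit, so C − K cannot be calculated.
- Between patients, the only thing randomization varies is which side gets CDO. If overall pain does not depend on which breast hurts, then g(C, K) = g(K, C), and left-treated and right-treated patients have the same expected score whatever the CDO effect. With S = (C + K)/2, for example, the expected difference is 0.
- Over time, S at week 4 minus S at baseline contains recovery in both breasts, and no patient is without CDO.

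None of these three routes gives a CDO-versus-control contrast.

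**Step 2. Count of ratings, with N = 30 from G1 and full attendance.**

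| Reading of F2 | Ratings | CDO-control pairs |
|---|---|---|
| One unsided score, baseline and week 4 | 30 × 2 = 60 | 0 |
| One unsided score, Visits 1–4 | 30 × 4 = 120 | 0 |
| One unsided score, baseline plus Visits 1–4 | 30 × 5 = 150 | 0 |
| Each breast rated, Visits 1–4 | 30 × 2 × 4 = 240 | up to 30 per visit |

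The last row gives 30 × 4 = 120 pairs in all. These are four repeated pairs on each of 30 patients, not 120 independent pairs.

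**Step 3. Schedule.** The overview sentence in F2 gives baseline and week 4. The pain entry gives every visit, and all four weekly visit descriptions list a pain questionnaire. The pain-specific text is therefore weekly, and the general sentence contradicts it. Baseline is the day of surgery. Its description in F2 covers consent, imaging at closure ("When the plastic surgeon closes the incision, the research coordinator will obtain the tissue oxygenation image"), dressing and device education, and lists no pain rating.

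**Step 4. Scale and status.** The F2 overview and G2 call the scale a visual analog scale, and the pain entry's title uses the abbreviation VAS, but the entry's text describes a numeric scale. A visual analog scale for pain is also listed in the optional questionnaires paragraph, so it is unclear whether the secondary outcome is mandatory.

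**Step 5. Pain during dressing change.** H3 concerns this moment, but F2 does not say whether pain is rated before, during or after the change. Nor is it clear that the control side has a matching event. Section C has the tape staying on for 3 weeks. The dressing-change paragraph of F2 has weekly changes for all patients. The Visit 1 to 3 descriptions specify replacement only of the CDO dressing.

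**The case against.** The strongest reply is that the single score is inferred from silence. The wound-photograph and tissue-oxygenation entries in F2 do not name a side either, and both are plainly local measures. F1 also refers to an attached table of measurements by visit, which is not among the text reviewed and might specify side. This stands as a caution, and the count of 0 pairs is conditional on the unsided reading. The inference is still a strong one. An image is necessarily of a particular site, whereas a patient's pain intensity is not. The same section states side explicitly where the authors want it, in the scar scales. A coordinator following the pain entry would record one number.

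A second reply is that the plan does provide for pain by side. It does, so it would be wrong to say that the trial cannot compare pain between breasts at all. But those items are optional, sit within scar-satisfaction scales and are not tied to dressing change.

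A reader might also infer from the overview sentence that pain is missed during the weeks when the dressing is worn and changed. The documents do not support that. The pain entry and all four visit descriptions are weekly, and Visit 4 is itself a dressing change and removal visit. Likewise, a reader might suppose that pain is near its floor by week 4. Section C says only that incisions are normally healed once the tape is removed at 3 weeks; it says nothing about pain.

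Finally, this is an exploratory pilot and pain is a secondary outcome. That limits the weight of the point but does not remove it, because a side not recorded at the visit cannot be recovered later.

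**Conclusion.** The point holds for the secondary-outcome pain rating. Read as written, it is one patient-level score per visit, gives 0 of 30 possible within-patient contrasts at each visit, and cannot test the pain part of H3. Rated by breast, it would give up to 30 pairs per visit.

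This rests on one assumption: that the absence of a named side in the pain entry means an unsided rating, and that the unseen measurement table does not say otherwise.

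The schedule, scale name and mandatory-or-optional status are contradictions within F2 that need reconciling. They do not show that pain goes unmeasured in weeks 1 to 3. The change should be made before further ratings are collected. It is not critical to the primary outcomes.

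**What to change.** 1. **F2, pain entry:** require pain to be rated separately for the left and right breast at each of Visits 1 to 4, on one named scale, and remove the pain VAS from the optional list.
2. **F2, overview:** bring the baseline-and-week-4 sentence into line with the weekly pain schedule in the pain entry and visit descriptions.
3. **G2:** name the within-patient CDO-minus-control difference as the pain outcome, analysed as paired repeated measures over weeks 1 to 4 with patient as the cluster.
4. **Dressing change:** reconcile Section C with the dressing-change paragraph and visit descriptions in F2 before defining a paired rating during dressing change. Until then, a paired rating at rest is the contrast clearly available on both sides. H3 should say which rating it refers to.

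**Cost.** One extra line on the pain form if a single condition is rated. If both rest and dressing change are rated, there are 2 × 2 = 4 ratings per visit. Visits are already planned at 50 minutes. Patients wear the device on one side and the plan describes no sham on the other, so the result should be labelled an unmasked patient report.
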